**Version 1.2**  
**21 December 2020**

No subjects enrolled.  
No effect on subject exposure or safety.

Based upon input from the Investigational Review Board, best corrected visual acuity and slit lamp exam were added to all visits prior to the baseline visit. This impacts several sections of the protocol including the Schema and Schedule of Activities section.

## STATEMENT OF COMPLIANCE

The trial will be conducted in accordance with International Conference on Harmonisation (ICH) Good Clinical Practice (GCP), applicable United States (US) Code of Federal Regulations (CFR), the Health Insurance Portability and Accountability Act (HIPAA), and local regulatory guidelines. The Principal Investigator will assure that no deviation from, or changes to the protocol will take place without prior agreement from the Investigational New Drug (IND) Sponsor, funding agency and documented approval from the Institutional Review Board (IRB), except where necessary to eliminate an immediate hazard(s) to the trial patients. All personnel involved in the conduct of this study have completed Human Subjects Protection and ICH GCP Training.

The protocol, informed consent form(s), recruitment materials, and all patient materials will be submitted to the IRB for review and approval. Approval of both the protocol and the consent form must be obtained before any patient is enrolled. Any amendment to the protocol will require review and approval by the IRB before the changes are implemented to the study. All changes to the consent form will be IRB approved; a determination will be made regarding whether a new consent needs to be obtained from patients who provided consent, using a previously approved consent form.

## 1 PROTOCOL SUMMARY

### 1.1 SYNOPSIS

- Title:** A Phase 2a Study of Safety, Tolerability, and Efficacy of Drug-Delivering Contact Lens LL-BMT1 in Patients With Primary Open-Angle Glaucoma or Ocular Hypertension
- Study Description:** This will be an open-label, phase 2a clinical study. Beginning 2 weeks prior to the Baseline Visit, all patients will have a 2-week run-in acclimation screening with a nonmedicated contact lens in each eye to ensure contact lens tolerability. Five patients with treated or treatment-naïve primary open-angle glaucoma (POAG) or ocular hypertension (OHT) in both eyes who have successfully passed the acclimation screening will be enrolled. All previously treated eyes will have a washout period prior to enrollment. At least one eye (called the study eye) will have untreated (after washout, if applicable) intraocular pressure (IOP) between 22 mmHg and 34 mmHg (inclusive). If the fellow eye does not meet this IOP criterion, it must have an untreated IOP (following washout, if applicable) within 5 mmHg of the study eye without exceeding the 34-mmHg maximum. Five patients will be enrolled to receive LL-BMT1 (medicated) contact lenses placed in a packaging solution containing [REDACTED]. During the 7-day treatment period, patients will be assessed for safety and IOP reduction. Adverse events (AEs) and treatment-related serious adverse event [SAE] will be monitored, as will other safety measures, including best-corrected visual acuity (BCVA), slit-lamp biomicroscopy, and contact lens protein deposit. The study hypothesis is that no safety concerns are revealed.
- Objectives:** The primary objective of this study is to evaluate the safety of LL-BMT1 in patients with POAG or OHT. Additional objectives of this study are to evaluate the tolerability and IOP-lowering effects of LL-BMT1 in patients with POAG or OHT.
- Endpoints:**  
*Primary safety endpoint:* AE rate  
*Secondary safety endpoints:* percent of patients with  $\geq 5$ -mmHg increase from baseline in IOP at each visit; abnormal slit-lamp biomicroscopy findings at the Baseline, Day 1, and Day 7 Visits; contact lens protein deposits at the Day 7 Visit; and change from baseline in Contact Lens Dry Eye Questionnaire-8 (CLDEQ-8) results at the Day 7 Visit  
*Secondary efficacy endpoints:* change from baseline in IOP at each visit

Study Population:	Five patients who are at least 18 years of age of either sex with POAG or OHT in both eyes
Phase:	2a
Description of Site Enrolling Patients:	Up to 2 sites within the United States (US)
Description of Study Intervention:	LL-BMT1 is a US Food and Drug Administration (FDA)-classified Group 4 extended-wear contact lens that has bimatoprost printed onto the anterior surface of the contact lens in one set concentration. The coating of the anterior surface does not obstruct the optic zone, and the bimatoprost elutes from both the concave and convex surfaces of the lens. LL-BMT1 is designed to lower the IOP of patients with POAG or OHT and be worn for 1 week (7 days, 6 nights). Patients will wear LL-BMT1 lenses for 1 week.
Study Duration:	3 to 4 months
Patient Treatment Duration:	1 week for each patient

## 1.2 SCHEMA

### **Day -45 to -14 (Visit 1): Screening**

- Total n=5 to 7 (If all 7 patients successfully complete the acclimation screening, only 5 patients will be enrolled to receive LL-BMT1. If dropouts occur during acclimation screening resulting in less than 5 patients successfully completing the acclimation screening, then that patient(s) will be replaced until at least 5 patients have been enrolled to receive LL-BMT1)
- Obtain informed consent
- Screen potential patients by inclusion and exclusion criteria, including:
  - Ultrasound pachymetry to assess corneal thickness
  - Humphrey visual field to assess visual field loss (*If Humphrey visual field assessment has been completed within 6 months of Screening Visit, it does not have to be repeated at the Screening Visit*)
- Obtain medical history
- Concomitant medications - *Systemic treatments that the patient has been receiving for at least 30 days prior to study initiation will be collected*
- If on any IOP-lowering medication, start washout according to the period required for the current medication, timed to end at the Baseline Visit
- Two weeks prior to the Baseline Visit, start 2-week acclimation screening with insertion of nonmedicated lenses

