**Day -7 (Visit 3): Acclimation (first nonmedicated lens removal)**

- Concomitant medications
- AEs - The patient will also be questioned about AEs related to the contact lens wear by the investigator. Eligibility for the treatment portion of the study will be at investigator's discretion.
- Nonmedicated lens removal
- BCVA
- Biomicroscopy

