## 5.2 EXCLUSION CRITERIA

An individual who meets any of the following criteria will be excluded from participation in this study:

1. Glaucoma or optic neuropathy due to anything other than POAG or OHT
2. Cup-to-disc ratio of  $>0.8$  in either eye
3. Corneal thickness  $<480$  or  $>620$   $\mu\text{m}$
4. IOP  $>34$  mmHg in either eye at the Screening Visit or Baseline Visit
5. Significant visual field loss, in the opinion of the investigator
6. Uncontrolled systemic disease, such as poorly controlled hypertension or poorly controlled diabetes
7. An active ocular infection (ie, bacterial, viral, parasitic, or fungal) in either eye at the Screening Visit
8. Current contact lens use for vision correction (unless willing to switch to glasses for the duration of the study)
9. Current contact lens use for cosmetic purposes (unless willing to discontinue use for the duration of the study)
10. Clinically significant dry eye
11. History of treated allergic, vernal, or atopic conjunctivitis
12. History of contact lens intolerance, corneal scarring, corneal neovascularization, giant papillary conjunctivitis, or any other corneal pathology that is deemed by the investigator to constitute a contraindication for applying contact lenses
13. Aphakia or presence of anterior chamber intraocular lens in either eye
14. History of clinically significant macular pathology (ie, progressive age-related macular degeneration, diabetic macular edema, proliferative diabetic retinopathy, etc.)
15. History of corneal refractive surgery (ie, laser-assisted in situ keratomileusis [LASIK], photorefractive keratectomy [PRK], radial keratotomy [RK], small incision lenticule extraction [SMILE], or corneal inlay, etc.)
16. History of prior incisional glaucoma surgery (ie, bleb, shunt, seton, etc.)
17. History within past 6 months of any ocular anterior segment laser or other intraocular surgery
18. Use of laser of any type on retina in either eye within 3 months prior to the Screening Visit
19. History of punctal cautery or planned use of punctal plugs during the study
20. Cataract surgery in either eye within 3 months, or other intraocular surgery in either eye within 6 months prior to the Screening Visit or planned during the course of the study

21. Anticipated need for ocular surgery in either eye during the study period

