#### 6.5 CONCOMITANT THERAPY

Aside from study medication, antihistamines and all topical ocular medications are prohibited during the study. In addition, marijuana and any other recreational drugs are prohibited. Systemic treatments that the patient has been receiving for at least 30 days prior to study initiation are

acceptable. The medical monitor should be informed of any new systemic medications that cannot be delayed until the end of the study to determine if the patient can participate and/or continue in the study. Prior to study treatment initiation, any current glaucoma medications must be washed out using the below schedule (but washout should not commence until after written informed consent has been obtained):

- 4 days washout for parasympathomimetic and topical or systemic carbonic anhydrase inhibitors
- 2 weeks washout for sympathomimetics and alpha agonists
- 4 weeks washout for beta adrenergic blocking agents, combination product, ROCK inhibitors, and prostaglandin agonists

---

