#### 6.5.1 RESCUE MEDICINE

The Sponsor will not supply rescue medication. Should the IOP at any time during the study be elevated 10 mmHg above baseline (after washout, if applicable), the lens will be removed and a different IOP-lowering medication should be prescribed at the discretion of the investigator. The patient will be discontinued from study intervention but will continue in the study.

The date and time of rescue medication administration as well as the name and dosage regimen of the rescue medication must be recorded in the electronic Case Report Form (eCRF).

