Unscheduled visits can be included if safety concerns arise. Additional examinations may be performed as necessary to ensure the safety and wellbeing of patients during the study. eCRFs should be completed for each unscheduled visit.

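### Patients on a 2- or 4-week washout have no required off-drug IOP reading before Day 0, although they attend clinic during it: a participant-protection gap

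*Protocol*

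**What the plan says.** **Timing of washout.** The Screening entry of the Schema (protocol Section 1.2) says: "If on any IOP-lowering medication, start washout according to the period required for the current medication, timed to end at the Baseline Visit". Section 6.5 sets the periods: "4 weeks washout for beta adrenergic blocking agents, combination product, ROCK inhibitors, and prostaglandin agonists"; "2 weeks washout for sympathomimetics and alpha agonists"; and 4 days for the remaining classes. It also bars washout before written consent, which is taken at Screening.

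**Visits during washout.** Patients attend on Day -14 (Visit 2), Day -7 (Visit 3) and Day -6 (Visit 4). The Schema lists acuity, biomicroscopy, adverse events, concomitant medication and handling of the nonmedicated lens. IOP is not listed. The IOP row of Section 1.3 is marked at Visit 1, blank at Visits 2 to 4, and next marked at Visit 5 (Day 0). The Version 1.2 summary records what the IRB asked for: "best corrected visual acuity and slit lamp exam were added to all visits prior to the baseline visit".

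**Pressure limits.** Exclusion criterion 4 (Section 5.2) sets a ceiling of 34 mmHg, which applies "in either eye at the Screening Visit or Baseline Visit". Section 6.5.1 adds: "Should the IOP at any time during the study be elevated 10 mmHg above baseline (after washout, if applicable), the lens will be removed".

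**Discretion.** Section 8.2 allows unscheduled visits and says: "Additional examinations may be performed as necessary to ensure the safety and wellbeing of patients during the study". At Visit 3, after questions about lens-related events, the Schema says: "Eligibility for the treatment portion of the study will be at investigator's discretion".

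**The concern.** Washout withdraws pressure-lowering treatment from patients with glaucoma or ocular hypertension for the sake of the trial. If the schedule is followed exactly, a rise in pressure after withdrawal is found before Day 0 only if an investigator chooses to measure it. The eye checks at the acclimation visits do not measure pressure.

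The protocol watches pressure more closely once treatment starts: IOP is scheduled on Days 1, 4, 7 and 8, never more than 3 days apart. It also foresees that an untreated eye may exceed 34 mmHg, since it excludes such eyes at Baseline, but it looks only when washout has ended. What is at stake is the protection of patients between withdrawal of therapy and Day 0.

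**Working it through.** No planned figure in the documents bears on this, so the check is a count of visits against washout windows.

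**Inputs**
- Washout lengths: 28, 14 and 4 days (protocol Sections 5.1 and 6.5).
- Washout ends on Day 0 (Section 1.2).
- Screening window: Day -45 to Day -14 (Section 1.3).
- Visits 2, 3 and 4: Days -14, -7 and -6, with no IOP. The Schema and the Section 1.3 table agree on this, so it is not an artefact of how the table was read.

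**Formulas**
- Washout start = 0 - washout length.
- Off-drug day of a visit = visit day - washout start.
- Longest gap = largest interval between successive points among the washout start, any scheduled off-drug IOP, and Day 0.

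| Class | Start | Visits 2, 3, 4 as off-drug days | Required off-drug IOP before Day 0 | Longest gap now |
|---|---|---|---|---|
| 4-week | Day -28 | 14, 21, 22 | 0 | 28 days |
| 2-week | Day -14 | 0 (start day), 7, 8 | 0 | 14 days |
| 4-day | Day -4 | none (all earlier) | 0 | 4 days |

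The Screening IOP does not fill the gap. It is taken before washout or on its first day. A 4-week washout needs Screening by Day -28, so the Screening IOP is 28 to 45 days before Day 0; for a 2-week washout it is 14 to 45 days before.

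**With IOP at Visit 2 (4-week class) and Visit 3 (both classes)**
- 4-week: readings on off-drug days 14 and 21; longest gap = max(14 - 0, 21 - 14, 28 - 21) = max(14, 7, 7) = 14 days.
- 2-week: reading on off-drug day 7; longest gap = max(7 - 0, 14 - 7) = 7 days.
- 4-day: no visit falls inside, so 4 days, unchanged.

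A reading at Visit 4 would come only one day after Visit 3 and would not shorten any longest gap.

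**Added assessments per patient**
- 4-week: 2 visits x 2 eyes = 4.
- 2-week: 1 visit x 2 eyes = 2.
- 4-day or treatment-naive: 0.

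For 5 to 7 patients the range is 0 to 7 x 4 = 28. At three measurements each (Section 1.3, footnote f) the maximum is 28 x 3 = 84 single readings, plus repeats of any value above the limit.

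**The case against.** The strongest reply has five parts.

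*The trial's results are untouched.* This stands. A reader might infer from the safety objective that the gap weakens the primary safety result. The documents do not support that. The objective concerns LL-BMT1, and the primary analysis counts events starting on or after the first insertion of the study lens (protocol Section 8.3.1, SAP Section 6.7). A rise found in washout would at most be an entry in the separate table of events before treatment.

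*No harm is shown.* This also stands. The documents give neither the frequency nor the size of pressure rises after washout. Exclusions for a cup-to-disc ratio above 0.8, significant field loss and a Screening IOP above 34 mmHg lower the risk.

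*The rescue rule is not defective.* Agreed. It could be read as failing because it has no reference value before Day 0. But it removes the lens and stops study treatment, so it belongs to the treatment phase. It simply offers no cover during washout.

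*Discretion and review already exist.* In part. Investigators may measure pressure, adverse events are asked about at each acclimation visit, and the IRB looked at these visits. It cannot be inferred that sites will fail to measure, or that the IRB overlooked pressure. But nothing requires a reading or names a value that prompts action. Nor do the documents say that the investigator restarts therapy when a patient fails during washout; Section 7.2 deals with the patient's own decision to leave.

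*The remedy is uneven and its threshold borrowed.* Fair. It leaves 14 days unmeasured in the 4-week class, the same gap that the 2-week class has now. The reason is practical: no visit falls there. The 34 mmHg figure is an eligibility ceiling, not a stated safety limit. It is also stricter than on-study rescue, where a patient enrolled at 34 mmHg would reach the rule at 34 + 10 = 44 mmHg. It is reused because a patient above it would be excluded on Day 0 if the pressure persisted.

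**Conclusion.** The gap is real and is a matter of participant protection only. Patients in the 4-week and 2-week classes have no required off-drug pressure reading before Day 0, despite three clinic visits after washout starts in the first class, and two in the second plus one on its start day. The figures of 28 and 14 days measure a monitoring gap, not harm.

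The count assumes that washout lasts exactly the stated period and ends on Day 0, that visits fall on their target days, and that no discretionary reading is taken. How many patients it touches depends on prior treatment: none if all five are treatment-naive, all if every one comes off a 2- or 4-week drug. The change is worth making because it is cheap and uses existing visits.

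**What to change.** **Schedule (Sections 1.2 and 1.3), for patients in washout only**
- Visit 3 (Day -7), 2- and 4-week classes: add IOP in both eyes after lens removal and after acuity and biomicroscopy.
- Visit 2 (Day -14), 4-week class: add IOP in both eyes after acuity and biomicroscopy and before lens insertion.
- Take both at 9 am +/-1 hour, the window of the qualifying Baseline reading.
- Use the mean of three measurements, as in footnote f. Name this rule in the text, because Section 8.2 gives a different one (mean of two, or median of three if the first two differ by more than 2 mmHg).

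**Action (exclusion criterion 4)**
- Extend it to these visits. A mean IOP above 34 mmHg in either eye, confirmed by a repeat assessment at the same visit, is a screen failure, and the investigator restarts IOP-lowering therapy.
- Leave lower values of concern to the investigator with the medical monitor.

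**Cost**
- The extra assessments counted above, with the existing tonometer at existing visits. Each patient screened beyond seven adds 0, 2 or 4.
- Morning booking of Visit 3, and of Visit 2 for the 4-week class.
- Some earlier screen failures, which Section 5.4 does not allow to be rescreened. These may include a patient who would have measured 34 mmHg or less on Day 0.
- The first 14 days of a 4-week washout remain unmeasured.

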### **Day -14 (Visit 2): Acclimation (first nonmedicated lens insertion)**

- Concomitant medications - *The medical monitor should be informed of any new systemic medications that cannot be delayed until the end of the study to determine if the patient can participate and/or continue in the study*
- AEs
- BCVA
- Biomicroscopy
- Nonmedicated lens insertion

**Day -7 (Visit 3): Acclimation (first nonmedicated lens removal)**

- Concomitant medications
- AEs - The patient will also be questioned about AEs related to the contact lens wear by the investigator. Eligibility for the treatment portion of the study will be at investigator's discretion.
- Nonmedicated lens removal
- BCVA
- Biomicroscopy

**Day -6 (Visit 4): Acclimation (second nonmedicated lens insertion)**

- Concomitant medications
- AEs
- BCVA
- Biomicroscopy
- Nonmedicated lens insertion (new lens)

**Day 0 (Visit 5): Baseline**

- Concomitant medications
- AEs - The patient will also be questioned about AEs related to the contact lens wear by the investigator. Eligibility for the treatment portion of the study will be at investigator's discretion.
- Remove nonmedicated lenses
- Verify inclusion/exclusion criteria
- CLDEQ-8
- Heart rate and blood pressure
- Urine pregnancy test for women of childbearing potential
- BCVA
- Biomicroscopy
- IOP (measured at 9 am  $\pm$ 1 hour)
- IOP (measured at 4 pm  $\pm$ 1 hour)

**Day 1 (Visit 6): Lens insertion**

- Concomitant medications
- AEs
- Heart rate and blood pressure - *procedure should be performed before study intervention*
- BCVA - *procedure should be performed before study intervention*
- Biomicroscopy - *procedure should be performed before study intervention*

- IOP (measured at 8 am  $\pm$ 1 hour) - *procedure should be performed before study intervention*
- LL-BMT1 insertion of new lens
- Contact lens assessment
- LL-BMT1 removal (directly before 4 pm IOP assessment) - *If a lens is damaged during removal, a new lens cannot be inserted in the patient's eye. Patients can remain on the study if at least one LL-BMT1 lens is able to be reinserted.*
- IOP (measured at 4 pm  $\pm$ 1 hour)
- LL-BMT1 reinsertion (directly after 4 pm IOP assessment)

#### **Day 4 (Visit 7): On-treatment assessment**

- Concomitant medications
- AEs
- Heart rate and blood pressure
- BCVA
- Biomicroscopy
- LL-BMT1 removal (directly before 8 am IOP assessment) - *If a lens is damaged during removal, a new lens cannot be inserted in the patient's eye. Patients can remain on the study if at least one LL-BMT1 lens is able to be reinserted.*
- IOP (measured at 8 am  $\pm$ 1 hour)
- LL-BMT1 reinsertion (directly after 8 am IOP assessment)

#### **Day 7 (Visit 8): End of treatment assessment**

- Concomitant medications
- AEs
- Heart rate and blood pressure
- BCVA
- Biomicroscopy
- LL-BMT1 removal - *Lens will be removed prior to IOP assessment, but the lens will not be reinserted*
- Contact lens protein deposit assessment
- IOP (measured at 4 pm  $\pm$ 1 hour)
- CLDEQ-8

#### **Day 8 (Visit 9): Follow-up assessment / End of study**

- Concomitant medications
- AEs
- BCVA
- Heart rate and blood pressure
- IOP (measured at 8 am  $\pm$ 1 hour)
- If patient's IOP is decreased by  $\geq 3$  mmHg from baseline, schedule Visit 10. If not, Visit 9 is the end of the study

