#### **Day 9 (Visit 10): Conditional follow-up assessment (If a patient's IOP is decreased from baseline by $\geq 3$ mmHg at the Day 8 Visit) / End of study**

- Concomitant medications
- AEs

- Heart rate and blood pressure
- IOP (measured at 8 am  $\pm$ 1 hour)

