hIOP will be performed at 8 am  $\pm$ 1 hour and 4 pm  $\pm$ 1 hour.

iIOP will be performed at 8 am  $\pm$ 1 hour.

jIOP will be performed at 4 pm  $\pm$ 1 hour.

kQuestionnaire to be given at the end of the acclimation screening.

lLens will be inserted by the investigator after all assessments (except 4 pm IOP assessment) are complete.

mLens will be removed prior to and reinserted following IOP assessment. If a lens is damaged during removal, a new lens cannot be inserted in the patient's eye. Patients can remain on the study if at least one LL-BMT1 lens is able to be reinserted.

nLens will be removed prior to IOP assessment, but the lens will not be reinserted.

oAssessments will include contact lens centration, movement with blinking, and lens surface wettability/deposits, as described in ISO 11980:2012.

pThe patient will also be questioned about AEs related to the contact lens wear by the investigator. Eligibility for the treatment portion of the study will be at investigator's discretion.

qShould the IOP at any time during the study be elevated 10 mmHg above baseline (after washout, if applicable), the lens will be removed and a different IOP-lowering medication should be prescribed at the discretion of the investigator. The patient will be discontinued from study intervention but will continue in the study

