Five (5) patients will receive LL-BMT1 contact lenses [REDACTED] inserted into each eye at the Day 1 visit, where they will remain until the Day 7 Visit, at which time the lenses will be removed. Patients will not remove the lenses themselves during the study. During the 7-day treatment period, patients will be assessed for safety and IOP reduction which requires removal and reinsertion of LL-BMT1 on Day 1 and Day 4. AEs will be monitored, as will other safety measures, including BCVA, slit-lamp biomicroscopy, and contact lens protein deposit. Patients will attend a follow-up visit on Day 8, during which heart rate/blood pressure, BCVA, and IOP will be assessed. If a patient's IOP is decreased from baseline by  $\geq 3$  mmHg at the Day 8 Visit, a Day 9 Visit will be performed in order to reassess IOP.

The primary focus of this safety study will be a comprehensive descriptive assessment of safety endpoints. No formal study hypothesis will be tested.

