#### 4.2 SCIENTIFIC RATIONALE FOR STUDY DESIGN

This study is designed to examine the use of bimatoprost delivered via extended-wear contact lenses and assess the safety and efficacy of this drug device in a sample of patients. Both bimatoprost and the contact lens (as a nonmedicated lens) are FDA-approved, long-standing commercial products with well-characterized safety and effectiveness profiles. All patients will attend a follow-up visit on Day 8, and if IOP at that visit is decreased from baseline by  $\geq 3$  mmHg, patients will attend a conditional follow-up visit on Day 9 in order to reassess IOP.

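### Day 9 IOP is measured only after a Day 8 fall of at least 3 mmHg: a Day 8 rise gets no required recheck, and by-visit Day 9 summaries are favourable by construction

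*Protocol*

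**What the plan says.** The trigger for Visit 10 appears in four places, and all agree. Protocol 1.2 (Day 8) sets it at a fall from baseline of at least 3 mmHg and then says "schedule Visit 10. If not, Visit 9 is the end of the study". The Day 9 entry is titled "Conditional follow-up assessment (If a patient's IOP is decreased from baseline by" that amount. Section 4.1 says that after such a fall "a Day 9 Visit will be performed in order to reassess IOP", and section 4.2 that "patients will attend a conditional follow-up visit on Day 9 in order to reassess IOP".

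A rise in IOP from baseline, assessed by visit, is a secondary safety endpoint. The threshold is 5 mmHg in Protocol 1.1 and 9.4.2 and in SAP 5.2 and 6.8, but 10 mmHg in Protocol 3. Change from baseline in IOP by visit is the secondary efficacy endpoint (Protocol 9.4.3, SAP 6.8). SAP 3.3 gives Visit 10 its own row in the table of analysis windows, and SAP 6.3 rules out imputation.

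The rescue rule in Protocol 6.5.1 and footnote q of 1.3 begins "Should the IOP at any time during the study be elevated 10 mmHg above baseline". It calls for lens removal and a different IOP-lowering drug, and adds "The patient will be discontinued from study intervention but will continue in the study". On Day 7, "Lens will be removed prior to IOP assessment, but the lens will not be reinserted". Under section 6.5, "antihistamines and all topical ocular medications are prohibited during the study".

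**The concern.** Safety is the primary objective, and previously treated eyes have been washed out for up to 4 weeks. The only conditional IOP reassessment nevertheless follows up the patient whose pressure is low. Baseline IOP may be as high as 34 mmHg, so a rise of 9 mmHg would mean 34 + 9 = 43 mmHg on Day 8, with no numeric rule acting on it and no required second reading.

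The second issue is reporting. Day 9 attendance depends on the Day 8 value of the variable being summarised. A mean change or a percentage with a rise at Day 9, set in a table beside Days 1, 4, 7 and 8, would describe a different and favourably selected group. A reader could take it as evidence that the effect lasts two days after lens removal.

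**Working it through.** **1. The visit rules applied to possible Day 8 changes** (thresholds from the documents; no assumptions).

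| Day 8 change, mmHg | Visit 10 now | Rise endpoint at 5 | Rescue rule at 10 | Visit 10 with the fix |
|---|---|---|---|---|
| -6, -3 | yes | no | no | yes |
| -2, 0, +4 | no | no | no | no |
| +5, +9 | no | yes | no | yes |
| +10, +12 | no | yes | yes | yes |

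No rise triggers Visit 10, whichever endpoint threshold is used. Rises from 5 to under 10 mmHg have no numeric action rule.

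**2. What selection does to Day 9.** The documents give no SD, so I assume an SD of change in one eye of 2.5, 3.0 or 3.5 mmHg, normal changes and no true change. Write D8 and D9 for the changes at Days 8 and 9. Both subtract the same baseline. With equal, independent visit variances v, each change has variance 2v and their covariance is v, so the correlation is v/2v = 0.5.

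- E[D8 | D8 ≤ -3] = -SD × φ(3/SD) / Φ(-3/SD)
- E[D9 | D8 ≤ -3] = 0.5 × that value

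| SD | φ(3/SD) | Φ(-3/SD) | Mean D8 in those selected | Expected mean D9 |
|---|---|---|---|---|
| 2.5 | 0.1942 | 0.1151 | -4.22 | -2.11 |
| 3.0 | 0.2420 | 0.1587 | -4.58 | -2.29 |
| 3.5 | 0.2763 | 0.1957 | -4.94 | -2.47 |

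An unselected group would have mean 0. The percentage with a rise shifts the same way. P(D9 ≥ 5 | D8 ≤ -3), from the bivariate normal with correlation 0.5, is 0.07%, 0.31% and 0.83%. Without selection, 1 - Φ(5/SD) is 2.3%, 4.8% and 7.7%.

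In this no-effect case the Day 9 group is also very small: 5 × Φ(-3/SD) = 0.58, 0.79 and 0.98 patients expected, taking the study eye as the trigger. A real drug effect would enlarge the group, but it would still be selected.

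**3. Load from adding a rise trigger at +5 mmHg.** On the same SDs, p = 1 - Φ(5/SD) = 0.0228, 0.0478, 0.0766 per eye. The chance that either eye triggers is 2p - P(both).

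| Correlation between eyes | Either eye, per patient (SD 2.5 / 3.0 / 3.5) | At least one of 5 patients |
|---|---|---|
| 0 | 0.045 / 0.093 / 0.147 | 21% / 39% / 55% |
| 0.5 | 0.041 / 0.084 / 0.131 | 19% / 36% / 50% |
| 0.8 | 0.036 / 0.072 / 0.112 | 17% / 31% / 45% |

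The expected number of extra visits is 5 × the per-patient chance: from 0.18 (SD 2.5, correlation 0.8) to 0.74 (SD 3.5, correlation 0). Because no true change is assumed, these are all chance triggers.

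**4. Whether the recheck would tell anything.** For an eye left untreated, P(D9 ≥ 5 | D8 ≥ 5) is 18%, 24% and 29% if there is no true rise, and 85%, 83% and 81% if a true rise of 7 mmHg (an illustrative value) persists. A second reading therefore separates the two cases fairly well.

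**The case against.** The case on the other side is substantial.

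- **The rule is consistent and has a purpose.** Visit 10 plausibly tracks residual drug effect after lens removal. This stands: nothing here is a contradiction. It explains the trigger for falls, but gives no reason to leave rises out.
- **There is cover for a rise.** A reader might infer that a patient with a Day 8 rise is simply let go. The documents do not support that. Clinically significant findings become AEs, and unscheduled visits and further examinations are allowed (8.2). AEs are followed until resolved or stable, and patients are told to call about later events (8.3.4). An IOP event can hardly be judged stable without measuring IOP. What remains is that the first step is a judgement, with no threshold or date.
- **The rescue rule still works on Day 8.** A reader might infer that it lapses because the lens is already out, or that it conflicts with ending at Visit 9. Only lens removal is moot; the instruction to prescribe another drug applies throughout the study.
- **Adding Visit 10 creates a problem of its own.** A patient who ends at Visit 9 is free of the ban on topical drugs; keeping that patient to Day 9 extends it. This is right, so the fix must permit treatment. A Day 9 reading after treatment then cannot confirm the rise.
- **The size depends on the threshold and the unit.** At 10 mmHg the chance that at least one of 5 study eyes triggers falls to 0.02%-1.1%, where rescue already acts. Protocol 8.2 also averages the two eyes for patient-level change, so the unit of the present trigger is unclear. Both points stand, and the 5-versus-10 conflict has to be settled anyway.
- **Day 9 is already labelled conditional, listings are planned and nothing is formally tested.** True, but neither document exempts Day 9 from the by-visit summaries.

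**Conclusion.** Both parts hold, as an inexpensive improvement that should be made rather than an error in the plan. The reporting point is the firmer one. Its direction needs only a positive correlation between the Day 8 and Day 9 changes; its size, about -2.1 to -2.5 mmHg with no true effect, rests on the assumed SDs and a correlation of 0.5. The follow-up gap is read straight from the text and needs no assumed figure. It is narrow: rises of 5 to under 10 mmHg have neither a numeric action rule nor a required recheck, while larger rises have a treatment rule but no required recheck.

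A reader might also infer that the safety endpoint is miscounted or a test compromised. Neither follows: the Day 8 count is the same with or without Visit 10, and no hypothesis is tested.

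**What to change.** 1. **Protocol 1.2 (Day 8 and Day 9), 4.1 and 4.2.** Also schedule Visit 10 when Day 8 IOP in either eye is at least 5 mmHg above baseline, after settling that threshold with section 3. State there, with a matching exception in 6.5, that for such a patient IOP-lowering treatment may start once the Day 8 reading is taken, need not wait for Visit 10 and is not a deviation. Flag Day 9 values taken after treatment.
2. **SAP 6.8.** Add one sentence: Day 9 IOP is presented only as a listing of conditionally followed patients, with no by-visit mean change or percentage. This is needed even with the first change, because on the same assumptions 73%-86% of study eyes lie between -3 and +5 mmHg on Day 8 and trigger neither rule, so Day 9 remains a selected group.

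The cost is an IRB-approved amendment, one SAP sentence and about 0.2-0.7 expected extra short visits from chance alone, plus any true rises. No new visit type or procedure is needed. The change adds follow-up only: it does not alter the Day 8 endpoint count, and a treated patient's Day 9 value does not show whether the rise would have persisted.
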